Protocol:

Impact of Pillboxes on Medication Adherence

IRB-18-0451

NCT03861845

Primary Investigator:

[name], OTR/L, Assistant Professor

Occupational Therapy Department

Florida International University

[contact]

Email: [contact]

Version:

3

Date:

February 2019

SUMMARY OF THE RESEARCH.....	3
BACKGROUND.....	4
Scientific Background & Literature Review.....	4
RESEARCH OBJECTIVES.....	5
SUBJECT POPULATION.....	6
Duration of participation.....	6
Number of Participants.....	6
Inclusion & Exclusion Criteria.....	6
SUBJECT RECRUITMENT.....	7
Identification of Subjects & Recruitment.....	7
Incentives.....	7
METHODS & ACTIVITIES.....	8
Instrumentation & Data Collection.....	8
Intervention.....	9
Interactions.....	10
Data Analysis.....	11
BENEFITS & RISKS.....	12
Benefits to Subjects.....	12
Benefits to Society and/or Others.....	12
Reasonably Expected Risks, Harms, and/or Discomforts.....	12
Minimizing Risks, Harms, and/or Discomforts.....	12
INFORMED CONSENT.....	13
CONFIDENTIALITY & PRIVACY.....	14
Provisions to Protect Privacy.....	14
Confidentiality of Data.....	14
Breaking Confidentiality.....	14

SUMMARY OF THE RESEARCH

This study uses an experimental design to test the impact of different types of pillboxes on medication adherence. Participants in this study will be randomized to receive one of the three pillbox interventions: 1) A standard seven day a week, one-dose per day pillbox with training 2) an off-the-shelf pillbox that was purchased specifically for the individual's needs with training and education, or 3) a customized 3D printed pillbox that was designed and manufactured specifically to the individual's needs with training and education. Participants will have three visits with the research team to collect baseline data, receive the pillbox, and collect follow up data.

Risks to the study include loss of time, boredom, invasion of privacy, and medication errors. We have taken precautions to mitigate these risks. This study will improve understanding of medication adherence and potentially help us better address poor medication adherence which needlessly causes morbidity, mortality, and costs over \$300 million in unnecessary healthcare costs each year.

BACKGROUND

Scientific Background & Literature Review

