Many individuals do not take medicine as prescribed resulting in declines in health and function. Pillboxes are a cost effective and easy to implement intervention that can help people better take their medications as prescribed. While some studies find that pillboxes can increase medication adherence as much as 5% other studies find that pillboxes have no effect. We hypothesize that to be effective pillboxes must be customized to the client's needs and be part of a package of services involving training on the device and education. The purpose of this study is to understand the impact of customized pillboxes on medication adherence.

1. Vlasnik, J. J., Aliotta, S. L., & DeLor, B. (2005). Medication adherence: factors influencing compliance with prescribed medication plans. *The Case Manager*, 16(2), 47-51.
2. Bartlett, R. J. (2018, September). Characteristics of Adults Managing Vitamins/Supplements and Prescribed Medications- Who Is Using, Not Using, and Abandoning Use of Pillboxes?: A Descriptive Study. *PubMed*, 32(5), 231-239. doi: 10.1097/NUR.0000000000000395
3. Defanti e Souza, F. and da Silva Santana, C. (2013) A descriptive study about the use of pillboxes by older adults. *Health*, 5, 103-109. doi: 10.4236/health.2013.512A014
4. Bartlett, R. J., Knisely, M. R., Boyer, K., & Pike, C. (2017). Pillbox intervention fidelity in medication adherence research: A systematic review. *Nursing Outlook*, 65(4), 464-476. doi:10.1016/j.outlook.2016.12.011

RESEARCH OBJECTIVES

The purpose of this study is to:

- Understand the impact of pillbox customization on medication adherence
- Understand the impact of pillbox customization on device satisfaction
- Test the feasibility of the research methodology

SUBJECT POPULATION

Duration of participation

Interaction 1: Screening: .5 hrs

Interaction 2: Informed Consent & Evaluation: 2 hrs

Interaction 3: Dispersion of pillboxes: 1 hr

Interaction 4: Follow-up Data Collection: 1.5 hrs

Total time commitment- approximately 5 hrs

Number of Participants

We seek to enroll as many as 40 participants in the study. This means we may screen as many as 120 individuals to identify the 40 study participants.

Inclusion & Exclusion Criteria

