To be included in this study participants must be 18 years of age or older, speak English, and be prescribed to take two or more medications per day, and manage their own medications.

Participants will be excluded if they have a significant cognitive impairment, unwilling to use a novel pillbox, or are unable to meet with the research team.

SUBJECT RECRUITMENT

Identification of Subjects & Recruitment

We will recruit through word of mouth, by sharing study information with local organizations that serve adults who take medications, and snowballing (asking participants to share the recruitment flyer with other individuals who take medications). We will also post electronic flyers on social media.

Incentives

Participants who complete all study procedures will earn up to \$20 in gift cards and a pillbox. On the 1st and 3rd visit, participants will receive a \$10 gift card. On the 2nd visit, the participant will receive a pillbox worth no more than \$15.

METHODS & ACTIVITIES

Instrumentation & Data Collection

Below is a description of each data collection tool.

- Screener Survey - ensures that the individual meets the eligibility criteria for the research study. This also allows the individual to describe their preferred contact method.
- Adherence to Refills and Medication Scale - 12 question Likert-like survey investigating medication adherence
- Demographics Questionnaire (Characteristics of Respondents [CORE] Survey) - Describes the participants background including race, ethnicity, gender, diagnoses, family situation, etc.
- Performance Assessment of Self Care Skills Medication Subtest - This performance-based assessment asks participants to sort a placebo medication. Participants are scored on their independence, safety, and adequacy in performing the task.
- Canadian Occupational Performance Measure - Participants discuss their daily routine. They score their performance of everyday activities on their importance, satisfaction, and performance.
- Quebec User Evaluation of Satisfaction with Assistive Technology - 12 item Likert-scale questionnaire evaluates how satisfied participants are with their assistive device and their related services that they experience.
- Medication Management Instrument For Deficiencies in the Elderly - Examines how much the participant knows about their medications, if they know how to take their medications, and if they know how to procure their medications. Also provides their complete medication list.

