- Exit Interview - Participants will be interviewed regarding their experiences within the study.
- Audio recordings - All interactions will be audio recorded. The PI will assess the researcher assistant's fidelity to the protocol.

Intervention

Participants in this study will randomized to receive one of the three pillbox interventions:

1. Standard Pillbox - Participants will receive a standard seven day a week, one-dose per day pillbox. The participant will receive basic training on using the pillbox.

Figure 1. Standard Pillbox

2. Off-the-Shelf Pillbox – Participants will receive an off-the-shelf pillbox that was purchased specifically for the individual’s needs from a store like CVS, Walgreens, or Amazon. The participant will also receive with training and education on using the pillbox.

3. Customized 3D printed Pillbox – The participants will receive a customized 3D printed pillbox that was designed and manufactured specifically to their individual needs.

Interactions

Research participants will occur in 4 interactions.

1. Screening

Up to .5 hrs on participant's own time on computer or the participant may be screened verbally at a time of their choosing
Assessments: screener survey

2. Informed Consent and Evaluation

Up to 2 hrs

Lab at FIU or preferred location where both parties (participants and evaluators) agree on
Assessments: COPM, QUEST, PASS, MedMaIDE, ARMS, and Demographics Questionnaire

3. Dispersion of pillboxes

Up to 1 hr

Lab at FIU or preferred location where both parties (participants and evaluators) agree on

4. Follow-up Data Collection

Up to 1.5 hrs

Lab at FIU or preferred location where both parties (participants and evaluators) agree on.

Data Analysis

Researchers will evaluate all variables using descriptive statistics. We will also explore the relationship between variables using approaches such as Pearson's product-moment correlation. Using this information, we will evaluate the appropriateness of the data against the assumptions for commonly used statistical approaches. Data may be normalized to increase appropriateness for the test. Then we will engage in means-testing using approaches such as t-tests, ANOVAs, Mann-Whitney U, Kruskal-Wallis analysis of variance, etc. as determined by looking at the appropriateness of the variable for that procedure. Specifically, we aim to compare means within and between groups on scores from the COPM & QUEST.

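### For COPM and QUEST, the plan does not make the randomized between-arm contrast the main one and does not say how baseline scores enter it

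*Combined protocol and SAP*

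**What the plan says.** Under Intervention: "Participants in this study will randomized to receive one of the three pillbox interventions". The Summary describes the schedule: "Participants will have three visits with the research team to collect baseline data, receive the pillbox, and collect follow up data". Under Interactions, the second contact, which precedes the dispensing of pillboxes at the third, carries "Assessments: COPM, QUEST, PASS, MedMaIDE, ARMS, and Demographics Questionnaire". Baseline COPM and QUEST scores are therefore planned. The fourth contact, follow-up, lists no instruments.

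The Data Analysis section gives the methods as an open list: "Then we will engage in means-testing using approaches such as t-tests, ANOVAs, Mann-Whitney U, Kruskal-Wallis analysis of variance, etc". The choice among them depends on how suitable each variable proves, and normalizing the data is allowed. The section then closes its quantitative part with "Specifically, we aim to compare means within and between groups on scores from the COPM & QUEST". Nothing else in the document says how these two instruments are to be compared.

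One of the Research Objectives is "Understand the impact of pillbox customization on device satisfaction". On size, the protocol says "We seek to enroll as many as 40 participants in the study". It states no allocation ratio, significance level, power, standard deviation or correlation.

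**The concern.** Two choices are left open that checks of distributional assumptions cannot settle.

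- **Which comparison carries the conclusion.** The customization objectives ask what customization does. The arms are randomized, so the between-arm contrast addresses that question. A change within one arm has no control. Naming both without an order leaves room to read a significant change in one arm and a non-significant change in another as a difference between pillbox types.
- **How baseline enters the between-arm contrast.** Follow-up scores alone, change scores and a repeated-measures analysis all fit the listed methods. Which unadjusted form is more precise depends on a correlation that nobody knows yet. With about 13 participants per arm, the choice could alter the conclusion.

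QUEST raises a further question. It rates an assistive device, but the eligibility criteria ask only that participants "be prescribed to take two or more medications per day, and manage their own medications", among other conditions that do not include owning a pillbox. The protocol does not say which device is rated before the study pillbox is given. If some participants have nothing to rate, a paired or change-score analysis would drop them.

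**Working it through.** The plan has no figure of its own to reproduce.

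**Inputs.** From the documents: three arms and at most 40 participants, so 40/3 = 13.3 per arm if allocation is equal. Assumed: 13 analysed per arm (N = 39), two-sided 5% level, normal data, equal SD at baseline and follow-up, and r = 0, 0.3, 0.5 or 0.7.

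**Variance of a pairwise difference**, in units of SD² × 2/13:
- follow-up only: 1
- change score: 2(1 − r)
- ANCOVA: (1 − r²) × 35/34. The factor 1 + 1/(3×12 − 2) = 35/34 = 1.029 is the cost of estimating the slope.

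| r | ANCOVA ÷ follow-up only | ANCOVA ÷ change |
|---|---|---|
| 0 | 1.029 | 0.515 |
| 0.3 | 0.91 × 1.029 = 0.937 | 0.65 × 1.029 = 0.669 |
| 0.5 | 0.75 × 1.029 = 0.772 | 0.75 × 1.029 = 0.772 |
| 0.7 | 0.51 × 1.029 = 0.525 | 0.85 × 1.029 = 0.875 |

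The last column is ((1 + r)/2) × 35/34. Simulation of 40,000 trials gave 1.026, 0.936, 0.770 and 0.527 for the first ratio.

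**95% CI half-width for a pairwise difference, in SD**, at r = 0.3 / 0.5 / 0.7:
- follow-up only: t(36) × √(2/13) = 0.80 at every r
- change: t(36) × √(2(1 − r) × 2/13) = 0.94 / 0.80 / 0.62
- ANCOVA: t(35) × √((1 − r²) × (35/34) × 2/13) = 0.77 / 0.70 / 0.58

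**Power of the 2-df arm test** if one arm is 1.0 SD higher (60,000 simulated trials), at r = 0 / 0.3 / 0.5 / 0.7:
- follow-up only: 72% throughout
- change: 41% / 56% / 72% / 91%
- ANCOVA: 70% / 74% / 83% / 95%

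**QUEST with some baseline scores missing.** Suppose 25% have no baseline device, at random. Keep them with a constant and an indicator, and let r apply to the rest. Simulated variance against follow-up only is then +5% / −2% / −14% / −33% at r = 0 / 0.3 / 0.5 / 0.7. Dropping them from the ANCOVA gives +42% / +30% / +8% / −27%. If 50% have none, keeping them gives +5% / +2% / −7% / −20%, and dropping them gives +135% / +115% / +79% / +20%. Both missing rates are assumed.

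**Within-arm tests when all arms truly change equally.** Let p be the power of a paired t-test with n = 13. For a change of 0.3 / 0.5 / 0.8 / 1.0 SD of the change, p = 0.169 / 0.382 / 0.754 / 0.911. The chance that some but not all of three arms are significant is 1 − p³ − (1 − p)³ = 42% / 71% / 56% / 24%. The ANCOVA arm test rejects in about 5% of the same trials.

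**The case against.** The strongest reply is that this is a small study with feasibility among its aims and an openly exploratory analysis section. On that view covariate choice is a refinement. A mixed repeated-measures ANOVA also fits the listed methods, and its group-by-time test is a between-arm test that uses baseline. That is fair, and it rules out one tempting inference: that the plan ignores or forbids baseline adjustment. It does neither. Feasibility is, however, one of three objectives. The other two concern the impact of customization, and the section commits to comparing means.

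Other stronger readings also go beyond the documents:
- *That within-arm p-values will be compared across arms.* Nothing says so. The 24% to 71% figures matter only if someone reads the results that way.
- *That an unadjusted between-arm comparison is biased, or that randomization guarantees it is not.* It is unbiased if all randomized participants are analysed. The section on minimizing risks removes participants who cannot explain and show correct pillbox use. That could happen after allocation and could differ by device. Baseline adjustment would not repair it.
- *That QUEST gains as much as COPM.* QUEST is the instrument tied to a stated objective, yet its baseline score may concern another device or none, so a low r is most plausible there. At r of 0 to 0.3 the indicator model runs from about +5% to −2% in variance, essentially no gain.
- *That some participants will have no baseline QUEST score.* This is inferred from the eligibility criteria. The schedule lists QUEST for everyone.

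Two criticisms of the remedy also stand. A linear model needs a fallback, because the plan already provides for failed assumptions. And one main analysis per score still leaves several scores unranked against each other.

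**Conclusion.** The point holds as a gap in pre-specification that is cheap to close; it is not a fatal flaw. The between-arm contrast should be named as the main one whatever the correlation, because the customization objectives require it. The case for adjusting by baseline is one of precision and depends on r. The reduction against follow-up scores alone is modest at 0.3 and substantial at 0.5 to 0.7; near zero there is a small loss. Against change scores ANCOVA is better at every r examined. The benefit is therefore mainly for COPM and may be negligible for QUEST.

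All sizes rest on assumed correlations, normal data and 13 analysed per arm. That number is a best case, since 40 is a ceiling, removals are possible and equal allocation is not stated. Follow-up COPM and QUEST scores are implied by the within-group comparison but not listed for the follow-up visit.

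**What to change.** In Data Analysis:

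1. State which COPM scores (importance, satisfaction, performance) are analysed. For each, and for QUEST, make the main analysis a between-arm comparison of the follow-up score adjusted for the same instrument's baseline score (ANCOVA). Report the 2-df arm test and the pairwise differences with 95% CIs.
2. Name a rank-based or transformed version to use if assumptions fail, in line with what the section already allows.
3. Report within-arm changes descriptively, and say that they are not evidence of a difference between arms.
4. For QUEST, first state which device is rated at baseline. If some participants have no baseline score, keep them in the between-arm model, for example with a constant and an indicator, rather than dropping them.

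The cost is wording only: the baseline scores are already scheduled, and no visit, instrument or participant is added. Each model spends one degree of freedom, or two for QUEST with the indicator. If r is near zero, variance rises about 3%, or about 5% for QUEST with the indicator. Extending the approach to the adherence scale (ARMS) would depend on its being collected at follow-up, which the protocol does not state.

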For qualitative data, we will use a grounded theory approach, consisting of open, axial, and selective coding to generate themes describing the participants answers to open ended questions.

BENEFITS & RISKS

Benefits to Subjects

There are no direct benefits to participants.

Benefits to Society and/or Others

Information learned from this study will be used to progress research and improve medication adherence for adults.

Reasonably Expected Risks, Harms, and/or Discomforts

Risk 1) Loss of time, low likelihood, low severity

Risk 2) Boredom, low likelihood, low severity

Risk 3) Invasion of privacy, low likelihood, low severity

Risk 4) Leakage of information, low likelihood, moderate severity Risk 5) Medication errors, low likelihood, moderate severity

Minimizing Risks, Harms, and/or Discomforts

Risk 1) Loss of time: Participants can select when and how they participate to limit loss of time related to travel. Research team will work with participants in an expedient manner.

Risk 2) Boredom: Participants will be informed that they can stop the survey or interview at any time. Participants will be informed that they can take breaks as needed during the survey or interview.

Risk 3) Invasion of privacy: Participants will be educated that they do not have to talk about topics or answer survey items that feel invasive.

Risk 4) Leakage of information: Electronic data will be stored on secure devices and servers. Identifying information (e.g., informed consent) will be stored separately from survey and interview data.

Risk 5) Medication errors: Participants will be required to verbalize how to use the pillboxes. They will also be required to correctly demonstrate how to use the pillboxes with placebo medication (i.e. tic-tacs or similar candy). Participants who cannot verbalize and demonstrate correctly use of the pillbox will be removed from study participation.

INFORMED CONSENT

Informed consent will be provided in a quiet and private environment. Participants will be given as much time as they need to consider participation and ask questions of the research team. Signed informed consent forms will be stored in the PI's office.

CONFIDENTIALITY & PRIVACY

Provisions to Protect Privacy

- Data will be de-identified
- Identified information (i.e. informed consents and the master key) will be stored separately from the study data.

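### Failing the pillbox check ends all participation, probably after allocation, and no count by arm is planned; the size and direction of any bias are unknown

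*Combined protocol and SAP*

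**What the plan says.** All places are in the combined protocol and SAP.

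- **Minimizing Risks, Harms, and/or Discomforts, Risk 5.** Participants must say how the boxes are used, and "They will also be required to correctly demonstrate how to use the pillboxes with placebo medication". The consequence of failing is: "Participants who cannot verbalize and demonstrate correctly use of the pillbox will be removed from study participation". No visit is named, and nothing is said about repeat attempts.
- **Summary of the Research.** "Participants will have three visits with the research team to collect baseline data, receive the pillbox, and collect follow up data".
- **Incentives.** "On the 2nd visit, the participant will receive a pillbox". Screening is not one of the three visits, so this is Interaction 3.
- **Interactions, Informed Consent and Evaluation (Interaction 2).** "Assessments: COPM, QUEST, PASS, MedMaIDE, ARMS, and Demographics Questionnaire". No pillbox training or pillbox check is listed. Interaction 4 lists no assessments at all.
- **Intervention.** For the standard box: "The participant will receive basic training on using the pillbox". The off-the-shelf arm gets training and education. The Summary says the same of the 3D-printed arm, although the Intervention text for that arm does not repeat it. The boxes in arms 2 and 3 are bought or made for the individual.
- **Data Analysis.** COPM and QUEST means are to be compared within and between groups. No analysis population, handling of removed participants, or count of removals by arm is given.

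**The concern.** A rule that ends participation after allocation, and whose trigger depends on the allocated device and training, can make the groups analysed differ from the groups randomised. If more people fail in one arm, and those who fail would have scored differently, part of a COPM or QUEST difference reflects who was left rather than what the box did. Any ARMS comparison would be exposed in the same way.

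There is a second loss that does not depend on bias. Testing the feasibility of the methodology is a stated objective. How many people in each arm cannot use the box they were given is a direct feasibility result for a study of customization, and the plan does not provide for it.

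**Working it through.** **1. When does the check fall?** The protocol does not say, so this is inference.

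- For hand-over after allocation: the check concerns use of the box; the box arrives at the second visit; the boxes in arms 2 and 3 are bought or made for the person, so the arm must be known before hand-over; Interaction 2 lists no pillbox check.
- For an earlier check: the PASS at Interaction 2 also uses placebo medication ("This performance-based assessment asks participants to sort a placebo medication"). But it is a separate scored assessment of sorting medication, not of using the study box.

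Hand-over is the likelier reading. An earlier check cannot be excluded.

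**2. Inputs.** The protocol gives a ceiling of 40 participants and three arms. It gives no allocation ratio, failure rate, SD, alpha or power, so there is no planned figure to reproduce. Assumed: 13 per arm (40/3, rounded down), no true effect, and a correlation r of 0.3, 0.5 or 0.7 between skill with the box and a raw follow-up score.

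**3. Shift if the k least skilled of 13 are removed from one arm and none from the other.** The expected values of the four lowest of 13 standard normal observations are -1.668, -1.164, -0.850 and -0.603. The mean skill of those remaining rises by (sum of the k lowest, sign reversed) / (13 - k). The bias is r times that rise.

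| Removed | Rise in mean skill | Bias, r = 0.3 | r = 0.5 | r = 0.7 |
|---|---|---|---|---|
| 1 v 0 | 1.668/12 = 0.139 | 0.04 | 0.07 | 0.10 |
| 2 v 0 | 2.832/11 = 0.257 | 0.08 | 0.13 | 0.18 |
| 3 v 0 | 3.682/10 = 0.368 | 0.11 | 0.18 | 0.26 |
| 4 v 0 | 4.285/9 = 0.476 | 0.14 | 0.24 | 0.33 |

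The standard error of a two-arm difference is sqrt(2/13) = 0.39 SD.

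**4. Variations.**

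- Imperfect selection (failure correlates 0.7 with skill) multiplies each entry by 0.7. For example, 2 v 0 becomes 0.05 to 0.13 SD.
- Equal counts (2 v 2) with unequal selection (1.0 v 0.7) still leave 0.2575 x 0.3 x r = 0.02 to 0.05 SD.
- Equal counts with equal selection give zero. So does a failure unrelated to outcome.
- Baseline scores reduce the shift in so far as skill relates to them too. If skill relates equally to baseline and follow-up, the shift cancels in a change score. With baseline adjustment, an assumed baseline-follow-up correlation of 0.5 and r = 0.7 at both times, 2 v 0 gives 0.2575 x (0.7 - 0.5 x 0.7) = 0.09 SD instead of 0.18.

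**5. Cross-check by another route.** Bias = (difference in share removed) x d, where d is the assumed gap in SD between those retained and those removed. For d = 0.5 to 1.5:

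- one extra removal gives 1/13 x d = 0.04 to 0.12 SD;
- two give 0.08 to 0.23;
- three give 0.12 to 0.35;
- four give 0.15 to 0.46.

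The ranges are comparable for one or two removals and wider at the top for three or four.

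**6. Would a removal occur at all?** At an assumed failure rate of 2% or 5%, the chance of at least one among 40 is 1 - 0.98^40 = 55% or 1 - 0.95^40 = 87%. This shows only that an unaddressed removal is plausible at low rates. It does not show bias.

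**The case against.** The case against has four parts.

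- **Every link is unstated.** Bias needs a check after allocation, a final pass or fail rather than teaching until correct, actual failures, different failures by arm, and failure related to outcome. The wording of the requirement also fits training to criterion, which could leave few or no removals. Eligibility points the same way: participants manage their own medications, and "Participants will be excluded if they have a significant cognitive impairment". This stands as a reason for a low grade. It does not answer the rule itself, which is explicit that failing ends participation.
- **The gap is general.** The plan has no missing-data rule for any dropout. True, but this loss is written into the protocol, is triggered by the device, and can be avoided for data collection at little cost.
- **The rule is a safety measure.** Stopping use of the box is for the investigators and is not questioned here. Collecting a follow-up score is a separate matter.
- **Follow-up of those removed does not repair everything.** This is right. QUEST rates satisfaction with the device in use, so bringing non-users back cannot restore that comparison; only COPM benefits.

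A reader might infer that the plan intends to analyse people outside their assigned arm. Nothing in the protocol says so; it simply does not say how those removed are treated.

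**Conclusion.** The concern holds as a minor one. The rule ends all participation, its timing relative to randomisation is not stated, and on the likeliest reading it can remove randomised participants unevenly, with no count by arm provided for. If the check precedes randomisation, the bias concern falls away.

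Three stronger readings are not supported:

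- **That the comparison is biased, or biased towards one arm.** The direction is unknown. Arm 1, with basic training only, could lose more weak users and look better; a harder device in arm 2 or 3 could do the same there.
- **That the effect is known to be small.** It looks small if one stops at 2 v 0. With 4 v 0 the order-statistic model reaches 0.33 SD, close to the 0.39 SD standard error, and the cross-check reaches 0.46 SD. Eligibility makes several failures in one arm less likely, but no failure rate is given.
- **That the check certainly follows allocation.** That is the likelier reading, not a stated fact.

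The figures rest on 13 per arm, no true effect, the assumed correlations and a raw follow-up score. Follow-up COPM and QUEST are themselves inferred from the Data Analysis section.

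**What to change.** 1. State at which visit randomisation and the check take place, with which box, and whether the check may be repeated. If the check precedes randomisation, report the number failing; nothing more is needed.
2. If it follows randomisation, leave the decision on use of the box to the investigators, but state that failing does not by itself end data collection and that those willing are invited to Interaction 4. State also that COPM is collected there.
3. Analyse COPM in the arm as randomised, using the baseline COPM from Interaction 2. Label QUEST as a comparison among users, with the number of non-users by arm.
4. Report failures by arm as a feasibility result. Describe the baseline scores (COPM, QUEST, PASS, MedMaIDE, ARMS) of removed and retained participants by arm. This needs no new visit and, with one or two removed per arm, can only be descriptive.

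**Cost.** A few sentences of protocol and consent wording. Each added follow-up takes up to 1.5 hours and a $10 gift card: two people cost up to 3 hours and $20; two in each of three arms (an assumption) cost up to 6 x 1.5 = 9 hours and $60. Some who fail will decline. If non-users gain nothing, an effect among users is diluted to 12/13 = 92% with one non-user in an arm, or 11/13 = 85% with two.
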